Protocol Outline

Protocol Title: Intraop Cone-beam CT for Percutaneous Nephrolithotomy

Protocol Date: August 23, 2021

Principal Investigator: [name], [name]

Research Team: [name], [name]

I. Abstract

Percutaneous nephrolithotomy (PCNL) is a first-line treatment for kidney stones >2cm. Frequently, patients require multiple procedures to address their stone burden. The decision to proceed with a second-look procedure is based on follow-up CT imaging, which is obtained postoperatively. In this study, we propose the use of a portable CT scan technology to obtain follow-up imaging while the patient is still under anesthesia for the initial procedure. The goal of this study is to determine whether this allows the surgeon to identify residual fragments and render the patient stone-free within a single anesthetic event.

II. Background and Significance/Preliminary Studies

Percutaneous nephrolithotomy (PCNL) is considered a first-line management option for kidney stones larger than two centimeters. Unfortunately, because of the large stone burden, up to 70% of these patients are left with residual stone fragments after their initial PCNL.¹ Additionally, an estimated 20% to 60% of such patients ultimately require further interventions due to residual stone fragments.² The need for a subsequent procedure is determined by postoperative abdominal computed tomography (CT) imaging, which is routinely performed on the first postoperative day at this institution. The decision to proceed with a second procedure is based on findings from this postoperative CT scan.

Cone-beam CT (CBCT) is a novel portable imaging technique that can allow cross-sectional imaging to be obtained intraoperatively, rather than post-operatively.³ Incorporating this modality would allow the surgeon to determine whether the procedure should be continued, in the event of residual fragments, or if it can be safely concluded. This would obviate the need for dedicated postoperative CT scans and, more importantly, reduce the need for subsequent procedures and consequently decrease the patient's length of stay.

III. Study Aims

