The purpose of this study is to determine whether using CBCT to perform an abdomen-pelvis CT scan immediately following initial PCNL, before the patient emerges from general anesthesia, allows the surgeon to determine whether additional work is needed or whether the procedure can be concluded without requiring further imaging or future interventions. Therefore, the primary outcome will be the rate of subsequent surgical intervention (i.e. "second-look" interventions) in patients undergoing CBCT.

IV. Administrative Organization

This study will be performed exclusively in the Main Operating Room area of Loyola University Medical Center.

V. Study Design

1. The study population will be patients undergoing initial PCNL, and they will be recruited to participate in this study prior to surgery.
2. Outcomes from this study will be compared with existing data on rates of second-look intervention at this institution.
3. **Our retrospective chart review of PCNL patients from 2018 and 2019 revealed a total of 178 PCNL patients, with a second-look intervention rate of 31.5%. We anticipate that use of CBCT will reduce our second-look intervention rate to 10%. However, despite being rendered radiographically stone-free with CBCT, we imagine patients may require second-look procedures for various reasons; we estimate the upper bound of this occurrence to be 15%. Assuming this, along with a power of 80% and a type I error rate of 5%, our study would be appropriately powered with 39 patients. We will aim to recruit 60 patients to allow for redundancy and unanticipated exclusions such as for reasons listed in VI.1.i.2.**

VI. Study Procedures

1. Subject selection procedures
 - i. Sampling plan
 1. Inclusion criteria:
 - a. Patients >18yo
 - b. Undergoing initial PCNL
 - c. **Stone fragmentation (laser/ultrasonic/mechanical) was performed during the procedure**
 2. Exclusion criteria:
 - a. **Patients who are deemed by the operating surgeon not to require any form of CT imaging, intra-operatively or post-operatively (for example, this can occur in the event of a single visible stone which is removed in its entirety under direct vision without requiring any fragmentation)**
 - b. Patients whose procedures are aborted for various reasons, including but not limited to bleeding, hemodynamic instability, equipment failure, and inadequacy of nephrostomy access
 - c. Patients whose habitus does not allow for the use of the CBCT machine
 - ii. Recruitment procedures

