 1. **Patients undergoing initial PCNL will be recruited and provided protocol/consent materials at a preoperative**

outpatient clinic visit. Consent will be obtained by one of the research team members at the preoperative visit or in the preoperative area on the day of surgery.

2. The patient will not be required to attend any additional clinical appointments beyond standard care. The patient will not be compensated for their participation in the study.
2. Data collection procedures
 - i. **A retrospective chart review of first-look PCNL procedures from 2018-2019 will be performed to identify a matched-cohort (based on patient demographics and stone characteristics) that meets the inclusion and exclusion criteria.**
 - ii. Data will be prospectively collected for our study cohort. The determination of our primary outcome (need for repeat surgical intervention) will be made in our usual fashion: via shared decision-making between the patient and the surgical team on the day subsequent to the initial procedure.
 - iii. Data collected for both cohorts will include but not be limited to:
 1. Demographic factors (age, sex, race/ethnicity)
 2. Medical factors (patient height and weight, presence of medical comorbidities, surgical history, pertinent laboratory values)
 3. Stone factors (location, size, composition, and other characteristics)
 4. Surgical factors (length of procedure, blood loss, operative time, length of hospital stay, radiation dose)
 5. Surgical complications, ranked by Clavien-Dindo class
 - iv. All data will be entered into Loyola's secure RedCAP application.

VII. Safety Monitoring Plan

1. There are no additional anticipated patient safety issues associated with performing intra-operative CBCT when compared to standard post-operative CT imaging.
2. In another study using the same Medtronic O-arm CBCT system that is available at Loyola, it has been demonstrated that the radiation dose experienced by the patient from CBCT is lower than that from standard CT imaging.⁴

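### Could exclusion b (aborted procedures) remove patients who have already had the cone-beam CT, and so flatter the CBCT second-look rate?

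*Combined protocol and SAP*

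**What the plan says.** Section VI.1.i.2.b excludes "Patients whose procedures are aborted for various reasons, including but not limited to bleeding, hemodynamic instability, equipment failure, and inadequacy of nephrostomy access". The list of reasons is open-ended and no time point relative to the scan is given.

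Two passages treat work after the scan as part of the same operation. Section II says "Incorporating this modality would allow the surgeon to determine whether the procedure should be continued, in the event of residual fragments". Section III says that CBCT "allows the surgeon to determine whether additional work is needed or whether the procedure can be concluded without requiring further imaging or future interventions".

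Other passages point to keeping scanned patients. Section III puts the scan directly after the initial PCNL, with the patient still anaesthetised, and defines the primary outcome as the rate of second-look "interventions) in patients undergoing CBCT".

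The exclusions are applied after consent, which is taken before surgery. Section V.3 sets 60 against a requirement of 39: "We will aim to recruit 60 patients to allow for redundancy and unanticipated exclusions such as for reasons listed in VI.1.i.2". Inclusion c ("Stone fragmentation (laser/ultrasonic/mechanical) was performed during the procedure") can likewise be judged only after the operation.

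For the comparison group, section VI.2.i plans a chart review "to identify a matched-cohort (based on patient demographics and stone characteristics) that meets the inclusion and exclusion criteria". Section II says of the standard postoperative CT: "which is routinely performed on the first postoperative day at this institution".

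**The concern.** If the post-scan work is part of the procedure, stopping it could count as aborting the procedure, and exclusion b would remove the patient. That patient has known residual stone and is probably more likely than the others to need a second look, so the removal would lower the CBCT rate.

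The historical group would have no matching loss. A comparable 2018-2019 patient would have finished the operation, been scanned the next day and stayed in the denominator. The decision to exclude would also fall to someone who might already know the scan result and the next-day decision about a second look. At stake is a bias towards CBCT in the primary comparison, from a criterion that appears neutral.

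**Working it through.** **Which reading the text supports**

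1. The outcome population is patients undergoing CBCT (section III). A scanned patient belongs to it by definition.
2. The scan follows the initial PCNL (section III). By then the operation named in inclusion b has reached its planned end, and what follows is extra work.
3. Exclusion a removes patients who need no CT, and exclusion c removes those whose habitus rules out the CBCT machine. Both concern patients who would not be scanned. Exclusion b fits that pattern as covering operations that never reach the scan, and inadequate access is a clear example.
4. Section VI.2.i applies b to the historical cohort as well, so aborts of the initial PCNL are removed on both sides. Only an abort in the added post-scan phase could be one-sided.

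**Size under the less natural reading**

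Inputs from the documents: 178 historical patients at 31.5% (0.315 × 178 ≈ 56 events), 60 recruited, chi-squared test, 5% level (taken as two-sided). Assumed: a share d of study patients dropped after the scan, and a share q of those needing a second look. The documents give neither.

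With no true effect, the analysed CBCT rate is (0.315 − d·q)/(1 − d). For d = 2% and q = 1: (0.315 − 0.02)/0.98 = 30.1%. The chance of a significant result favouring CBCT, by exact binomial enumeration without continuity correction, 60 v 178, is:

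| d | q = 0.315 | q = 0.5 | q = 1 |
|---|---|---|---|
| 0% | 2.3% | 2.3% | 2.3% |
| 1% | 2.3% | 2.5% | 2.9% |
| 2% | 2.3% | 2.6% | 3.6% |
| 5% | 2.3% | 3.2% | 6.8% |

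Against a 1:1 matched cohort (60 v 60) the figure is 2.6% with no drops, and 2.7-3.1%, 2.8-3.7% and 3.3-6.3% at d = 1%, 2% and 5% (q from 0.5 to 1). When dropping is unrelated to outcome (q = 0.315), nothing moves.

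**At the plan's own rates (section V.3)**

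For CBCT counts a and b (second look, none) and historical counts c = 56 and d′ = 122, χ² = N(a·d′ − b·c)² / (product of the four margins).

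- 9/60 (15%): 238 × (9·122 − 51·56)² / (60·178·65·173) = 6.13, p = 0.013. Dropping one second-look patient gives 8/59: 237 × (8·122 − 51·56)² / (59·178·64·173) = 7.20, p = 0.007.
- 6/60 (10%): p = 0.001. Dropping one gives 5/59: p = 0.0005.

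**Near the threshold**

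- 11/60 (p = 0.051) becomes 10/59 (p = 0.031). With continuity correction, 0.074 becomes 0.047.
- 12/60 (p = 0.089) becomes 10/58 (p = 0.036) if two are dropped. With correction, 0.125 becomes 0.054, so the switch disappears.
- 13/60 (p = 0.148) becomes 11/58 (p = 0.067) and stays non-significant.

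**The case for a change.** The best case for a change is that the two cues in section III show intent without settling the matter. An exclusion criterion would ordinarily override an outcome definition, and the plan defines no analysis set. The stated goal is to clear the stone under one anaesthetic, so a scanned patient whose continuation fails is a failure of the strategy and should count. One clause would settle this, and it is better settled before outcomes are known.

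Part of this stands. Exclusion b gives no time point, sections II and III use loose language about the procedure, and a post-scan loss, if it happened, would be one-sided. What does not follow is that the plan leads to a wrong analysis. The harmful reading has to set aside the outcome population and rests on descriptive sentences, neither of which is an eligibility rule.

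Nor is the clause a clear gain. If CBCT moves some stone clearance from before the scan to after it, late aborts would be kept in the CBCT group, while aborts during clearance in the historical group would still be excluded. That could put CBCT at a slight disadvantage.

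**Conclusion.** The concern does not call for a change. Exclusion b lacks a detail that an analyst would fill sensibly from the plan itself: it covers operations that never reach the scan, and otherwise eligible scanned patients are analysed.

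Harm would require the less natural reading, a material rate of post-scan aborts, and a second-look share among those patients above the general rate. The documents give no figure for either quantity. Over the assumed range of 1-5% dropped with half to all needing a second look, the false-positive chance favouring CBCT goes from 2.3% to between 2.5% and 6.8% (60 v 178). It exceeds 5% only at the extreme corner of that range. A significance conclusion changes only for results close to the 5% threshold, and not for the single-patient drops checked at the plan's 10% and 15%. The 60 − 39 = 21 spare places (35% of 60) cover redundancy and exclusions of every kind, and should not be read as an expected abort rate.

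### All controls come from 2018-2019, with no planned overlap with the CBCT patients, so a change in second-look practice over time could not be told apart from a CBCT effect

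*Combined protocol and SAP*

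**What the plan says.** The comparator is historical and from the same hospital. Section V.2 states: "Outcomes from this study will be compared with existing data on rates of second-look intervention at this institution". Section VI.2.i fixes its dates: "A retrospective chart review of first-look PCNL procedures from 2018-2019 will be performed to identify a matched-cohort", with matching "based on patient demographics and stone characteristics) that meets the inclusion and exclusion criteria". The chart review behind the planning figure covers the same two years and "revealed a total of 178 PCNL patients, with a second-look intervention rate of 31.5" per cent (V.3).

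The CBCT group comes later. Section VI.2.ii says "Data will be prospectively collected for our study cohort", and the header reads "Protocol Date: August 23, 2021". No enrolment start date appears.

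The primary outcome, need for a repeat intervention, is settled the next day between patient and surgical team, in the way that is customary at this hospital (VI.2.ii). Section VIII.1 compares the two groups on demographic and surgical factors. Section VIII.2 compares the two proportions with a chi-squared test that has no term for calendar period. The plan has no concurrent control, trend analysis, written re-operation threshold or stated limitation on this point.

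**The concern.** Every control belongs to one calendar period and every CBCT patient to a later one, so CBCT and period coincide completely. Anything that altered the second-look rate between the two periods (surgeons, instruments, willingness to re-operate) enters the VIII.2 comparison as if it were due to CBCT.

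Matching and the VIII.1 check act on patient, stone and surgical characteristics. They can make the groups look alike on those measures, but they say nothing about what the non-CBCT second-look rate would have been at the time of enrolment. The endpoint is open to such a shift because it is a clinical decision with no written threshold. If the background rate has fallen, CBCT gets credit it did not earn. If it has risen, a real benefit is hidden.

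**Working it through.** **Inputs.** From V.3: 178 historical patients, rate 31.5%; CBCT rate 15% for sizing; 39 patients needed, 60 to be recruited. From VI.2.i: controls from 2018-2019. From the header: 23 August 2021. Assumed, because the documents give no figures: a current non-CBCT rate of 25%, 20% or 38%, and 60 to 178 controls, since the size of the matched cohort is not stated.

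**1. The plan's own figures.** 56/178 = 31.5%, so the historical rate is consistent with its denominator. The 39 is closely matched by a one-sided, one-sample arcsine calculation of 15% against 31.5%:

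n = ((1.645 + 0.842)/h)², with h = 2·arcsin√0.315 − 2·arcsin√0.15 = 0.396, giving 39.3.

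The protocol does not name its formula. If this is the one used, it treats 31.5% as a known constant and allows for neither sampling error nor drift.

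**2. The gap.** From 31 December 2019 to 23 August 2021 is 366 + 235 = 601 days, and 601/30.44 = 19.7 months. This runs to the protocol date, not to a first patient.

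**3. Effect of drift on the VIII.2 test.** Let x of m controls and y of n CBCT patients have a second look, and let p̄ = (x + y)/(m + n). The uncorrected two-sided 5% test favours CBCT when

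(x/m − y/n) / √[p̄(1 − p̄)(1/m + 1/n)] > 1.96.

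CBCT is assumed to have no effect, so y follows the current non-CBCT rate while x follows 31.5%. The exact binomial probabilities of all (x, y) meeting the condition are summed, treating the groups as unpaired:

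| CBCT n | Current non-CBCT rate | 60 controls | 178 controls |
|---|---|---|---|
| 60 | 31.5% (no drift) | 2.6% | 2.3% |
| 60 | 25% | 12.5% | 14.7% |
| 60 | 20% | 30.9% | 39.6% |
| 39 | 25% | 10.5% | 11.1% |
| 39 | 20% | 25.1% | 28.5% |

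Hand check of the 39.6%: p̄ = (56.07 + 12)/238 = 0.286. The null standard error is √[0.286 × 0.714 × (1/178 + 1/60)] = 0.0675, and the standard error under drift is √[0.315 × 0.685/178 + 0.20 × 0.80/60] = 0.0623. Then Φ((0.115 − 1.96 × 0.0675)/0.0623) is about 0.39.

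**4. The other direction.** Suppose the current non-CBCT rate is 38% and CBCT truly lowers it by 16.5 points (the planned 31.5% minus 15%), to 21.5%. Tested against 31.5% with 60 CBCT patients, the benefit is detected in 24% of trials (60 controls) to 31% (178 controls). The same benefit without drift, 31.5% against 15%, is detected in 59% to 73%.

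**5. What recent controls would do.** If the controls share the current rate of 25% or 20%, the false-claim rate returns to about 2.5%. At the 2018-2019 volume, 178/24 = 7.4 patients a month, and 178/24 × 19.7 = 146 further charts up to the protocol date, before eligibility is applied. Comparing 146 such patients at 25% with 178 at 31.5% would show the drift in only about 25% of cases.

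**The case against.** A same-hospital historical control is an openly stated choice for a study of 60 patients. The background section ties the decision on a second procedure to the postoperative CT findings, the outcome is decided in the customary way at one centre, and VIII.1 compares surgical factors as well as demographics. The documents report no change in surgeons, equipment or threshold. All of this is fair and limits how much drift one should presume, but none of it supplies the non-CBCT rate at the time of enrolment.

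A reader might infer that every CBCT patient follows every control by at least 20 months. The documents do not support that: there is no enrolment date, and the interval to the protocol date is 19.7 months.

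A reader might also infer that the study question cannot be answered at all. That goes too far. The protocol says: "We anticipate that use of CBCT will reduce our second-look intervention rate to 10" per cent, which is 6 of 60. With no CBCT effect, 6 or fewer second looks in 60 has probability 0.3% at a current rate of 25% and 3.1% at 20%. Drift of this size would rarely imitate the result the protocol hopes for. It matters more for smaller differences: 9 or fewer of 60, the 15% used for sizing, has probability 4.5% and 21%.

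**Conclusion.** The concern holds as a weakness of design that the plan neither acknowledges nor offsets. Period and CBCT coincide, and no analysis in VIII can separate them. On the assumed falls to 25% or 20%, the false-claim rate with 60 CBCT patients rises from about 2.5% to 13-15% or 31-40%; a rise in the background rate would instead hide a benefit. These figures rest on assumed drift, unpaired groups and an assumed 60 to 178 controls. They show what the plan could not detect, not that practice has changed. The matter deserves an inexpensive improvement and a stated limitation, and it does not invalidate the study.

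**What to change.** In V.2 and VI.2.i, extend the chart review from 2018-2019 to the day before the first CBCT patient, with the same eligibility criteria and data form. Draw the matched controls for the VIII.2 test from the most recent pre-CBCT period first, for example the last 18-24 months, and keep 2018-2019 as a secondary comparison. Report the second-look rate by calendar period and, where available, in eligible PCNL patients treated without CBCT during enrolment, as a descriptive drift check only. State the remaining period confounding as a limitation.

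Two additions are not worth making. Matching on half-year is not possible, because pre-CBCT controls essentially never share a half-year with CBCT patients. Keeping the 178-control test and also requiring the CBCT point estimate to lie below the recent rate lowers false claims only from 14.7% to 13.8% (current rate 25%) or from 39.6% to 32.2% (20%).

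Cost: more chart abstraction and possibly ethics-board wording for non-participants' charts, with no extra patients, visits or procedures. The number of eligible recent charts is unknown (about 146 before eligibility if volume held), the drift check has low power, and confounding is reduced but not removed.

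### The matched historical controls are still to be chosen from 2018-2019 charts whose second-look results the team already holds, and the plan has no full selection rule, outcome masking or lock

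*Combined protocol and SAP*

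**What the plan says.** - **The control outcomes are already in hand.** Section V.3 is in the past tense: "Our retrospective chart review of PCNL patients from 2018 and 2019 revealed" 178 patients and a second-look rate of 31.5%.
- **The control group is not yet chosen.** Section VI.2.i is in the future tense and covers the same years: "A retrospective chart review of first-look PCNL procedures from 2018-2019 will be performed to identify a matched-cohort". The basis for the choice is "based on patient demographics and stone characteristics) that meets the inclusion and exclusion criteria".
- **The design section words the comparator differently.** Section V.2 states: "Outcomes from this study will be compared with existing data on rates of second-look intervention at this institution". That could mean the whole series.
- **The test.** Section VIII.2 compares the two second-look proportions by chi-squared, with no adjustment and no sensitivity analysis against the full pool. Section VIII.1 compares the cohorts on demographic and surgical factors.
- **What is not stated.** The plan does not give the specific matching variables, calipers, number of controls per CBCT patient, algorithm or tie rule. It does not say who selects the controls, whether that person can see second-look status, or when the list is closed.

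**The concern.** The control second-look rate is one of the two numbers in the primary comparison. A 31.5% rate cannot be computed without each patient's second-look status, so that status was abstracted before the plan was written. Choosing a subset afterwards, under a rule that leaves many subsets admissible, allows the outcome to influence who counts as a control, even without intent. The choice could also be made or revised once the CBCT results are known.

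The baseline comparison in VIII.1 would not reveal this, because a control set can be balanced on age, sex and stone size and still have been chosen with the outcome in view. The disagreement between V.2 and VI.2.i adds a second open choice, between the whole series and a matched subset. At stake is whether a reader can accept the primary p-value as coming from one fixed comparison.

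**Working it through.** **Inputs.** Pool of 178 with 31.5% second looks (V.3). CBCT rate 10% anticipated, 15% upper bound (V.3). CBCT sample 60 (recruitment target) or 39 (stated requirement); the point does not depend on how 39 was derived. Test: chi-squared on two proportions (VIII.2).

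**Assumptions, because the plan is silent.** One control per CBCT patient; all 178 eligible; no continuity correction; two-sided 5%.

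**Step 1: the plan's own figure.** 56/178 = 31.46%, which rounds to 31.5%. The pool therefore holds 56 events.

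**Step 2: how many control events reach p < 0.05.** With a CBCT events of n and b control events of m, and pooled proportion p̄ = (a+b)/(n+m),

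χ² = (b/m − a/n)² / [p̄(1−p̄)(1/n + 1/m)].

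Example, 9/60 v 18/60: p̄ = 27/120 = 0.225; χ² = 0.15² / (0.225 × 0.775 × 2/60) = 0.0225/0.0058125 = 3.87; p = 0.049.

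| CBCT | Controls just short | Controls that cross |
|---|---|---|
| 9/60 (15%) | 17/60, p = 0.076 | 18/60, p = 0.049 |
| 6/60 (10%) | 14/60, p just above 0.05 | 15/60, p = 0.031 |
| 6/39 (15.4%) | 13/39, p = 0.065 | 14/39, p = 0.038 |
| 4/39 (10.3%) | 10/39, p = 0.077 | 11/39, p = 0.044 |

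A continuity correction, which VIII.2 neither requires nor rules out, moves the 9/60 threshold from 18 to 20 events (19/60 gives p = 0.052).

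**Step 3: where an arbitrary control set would fall.** If n controls are drawn at random from the pool, events follow a hypergeometric distribution (178 patients, 56 events). For n = 60 the mean is 60 × 56/178 = 18.9 and the central 95% range is 13 to 25 (21.7% to 41.7%). For n = 39 it is 7 to 17. The share of random draws reaching the Step 2 threshold is:

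- 9/60: P(X ≥ 18) = 68%
- 6/60: P(X ≥ 15) = 93%
- 6/39: P(X ≥ 14) = 31%
- 4/39: P(X ≥ 11) = 75%

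This is chance variation between admissible control sets. It shows how near the boundary the result can lie. It does not measure selection bias, and masking would not shrink it.

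**Step 4: what choosing among sets could do (hypothetical).** Suppose there is no true effect (CBCT rate 56/178) and the most favourable of K independent random control sets is used. The chance of a significant result favouring CBCT is Σₐ Bin(a; n, 56/178) × [1 − F(c(a) − 1)^K]. Here c(a) is the Step 2 threshold for a CBCT events and F is the hypergeometric distribution function. For n = 39 it rises from 2.1% (K = 1) to 10.3% (K = 10). For n = 60 it rises from 1.7% to 8.7%. Nothing in the plan says that sets would be tried in this way; the figure only shows the direction and possible scale.

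**Step 5: no subset choice.** Against 56/178 the comparator is fixed. For 9/60: p̄ = 65/238 = 0.273; χ² = 0.1646² / [0.273 × 0.727 × (1/60 + 1/178)] = 6.12; p = 0.013. For 6/60, p = 0.001; for 6/39, p = 0.044; for 4/39, p = 0.007.

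The full pool is also more precise. Power = Φ[(0.165 − 1.96·SE₀)/SE₁] at 15% v 31.5%, where SE₀ and SE₁ are the pooled and unpooled standard errors:

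- 60 v 60: (0.165 − 1.96 × 0.0771)/0.0756 = 0.18, or 57%
- 60 v 178: (0.165 − 1.96 × 0.0665)/0.0578 = 0.60, or 73%

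**The case against.** A reader might infer that no selection rule exists and that the choice of controls alone will decide the primary result. The documents do not support either statement.

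- **The rule is incomplete, not absent.** VI.2.i fixes two matching domains and an eligibility screen, and the data list in VI.2.iii itemises age, sex, race/ethnicity and stone location, size and composition. This stands, but those items do not determine which charts are taken.
- **The fragility depends on the scenario.** At the anticipated rate with 60 patients (6/60), 93% of random draws are significant. With two controls per CBCT patient, 93% are significant even at 9/60, where the threshold is 34 of 120. This stands: the sharp sensitivity belongs to the 15% upper bound, or to 39 patients, under 1:1 matching.
- **Knowledge of individual outcomes by whoever selects is inferred.** V.3 gives an aggregate rate and no section names the abstractor or the selector. This stands in part. The patient-level data must exist, but the plan does not show that the selector has seen them, or any intent to use them.
- **Eligibility leaves less discretion than it seems.** The exclusion covering "Patients who are deemed by the operating surgeon not to require any form of CT imaging, intra-operatively or post-operatively" turns on the operating surgeon's view at the time, Section II says that postoperative CT was routine, and an aborted procedure would normally be on record. This largely stands. The clearest retrospective judgement is whether habitus would have allowed CBCT.
- **V.2 may already mean the full series.** If so, subset choice disappears. But VI.2.i describes a matched cohort, so the plan has to say which governs.

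**Conclusion.** The concern holds as an uncontrolled risk. The control outcomes were abstracted before the plan was written, the control set is to be chosen afterwards from the same years, and the plan has no complete rule, masking or lock, and no full-pool check. It does not show that selection has been or will be biased, and the random-draw figures are not an estimate of bias.

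The size depends on the CBCT result. At 9/60, one control event separates p = 0.076 from p = 0.049. At 6/60 the conclusion is fairly robust to which controls are drawn. With 39 patients it is sensitive at both 10% and 15%. All of this assumes 1:1 matching, an uncorrected test and all 178 eligible. The last is uncertain, because V.3 describes them only as PCNL patients, while VI.1.i requires an initial procedure with fragmentation. The plan should be amended before controls are selected, because outcome-aware selection cannot be undone afterwards.

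**What to change.** Amend VI.2.i and VIII.2 as follows.

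1. Report the CBCT second-look rate against all eligible 2018-2019 patients. This removes subset choice and uses more of the data already held.
2. If a matched set is kept, write and date the matching rule (variables, calipers, ratio, random seed). Code eligibility and run the matching on a file without second-look and other postoperative outcome fields. Lock the control list before CBCT outcomes are analysed, and only then merge outcomes.
3. Reconcile V.2 with VI.2.i by stating which comparator is primary and which is the sensitivity analysis.

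**Cost.** A paragraph in each section and an export without the outcome fields; no extra patients. Masking will be imperfect for staff who already know the charts, and charts read for eligibility may themselves show a second look, so a separate abstractor may be needed. Matching cannot be tuned once the list is locked. The full pool may be less balanced on covariates than a matched set, which is a reason to report both.
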